10.6 Subject Completion/Discontinuation

A subject is considered to have completed the study when he/she ceases active participation in the study because the subject has, or is presumed to have, completed all study procedures according with the protocol (with or without protocol deviations).

Reasons for completion/discontinuation will be reported on the Completion/Discontinuation eCRF, including: completed, screen failure, AE (eg, death), discontinuation by subject (eg, lost to follow-up [defined as 3 documented unsuccessful attempts to contact the subject], dropout), physician decision (eg, pregnancy, progressive disease, non-compliance with IP/protocol violation(s)), study terminated by sponsor, or other (reason to be specified by the investigator, eg, technical problems). Regardless of the reason, all data available for the subject up to the time of completion/discontinuation should be recorded in the appropriate eCRF.

Every effort will be made to have discontinued subjects complete the study completion/termination visit. If the completion/termination visit is done as an additional, unscheduled visit, the assessment results shall be recorded with the completion/termination visit. If a subject terminates participation in the study and does not return for the completion/termination visit, their last recorded assessments shall remain recorded with their last visit. The reason for discontinuation will be recorded, and the data collected up to the time of discontinuation will be used in the analysis and included in the clinical study report. If additional assessments are required, the assessments shall be recorded separately. Assessments to be performed at the termination visit (including in cases of withdraw or discontinuation) can be found in Supplement 20.3 Schedule of Study Procedures and Assessments and Supplement 20.4 Clinical Laboratory Assessments.

In the event of subject discontinuation due to an AE, clinical and/or laboratory investigations that are beyond the scope of the required study observations/assessments may be performed as part of the evaluation of the event. These investigations will take

place under the direction of the investigator in consultation with the sponsor, and the details of the outcome may be reported to the appropriate regulatory authorities by the sponsor.

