13.2.2 Full Analysis Set

The full analysis set will be the same as the safety analysis set. All efficacy analyses will be performed on the full analysis set.

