## 4.2 Safety Analysis Set (SAS)

The safety analysis set (SAS) is to comprise all subjects in the ENR with at least one BAX 855 infusion. All safety analyses are to be performed on the SAS.

Information on dosing with BAX 855 is to be obtained from the following eCRF panels:

- Study Infusion eCRF panels.
- *Infusion for Determination of Incremental Recovery* eCRF panels.
- Infusion for PK Assessment eCRF panels.
- *Minor Surgery* eCRF panels.

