#### 4.3 Full Analysis Set (FAS)

The full analysis set (FAS) is to comprise of all subjects in the SAS.

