## 6.7 Extent of Exposure

The following information is to be obtained from the eCRF:

- Information on study infusions (*Study Infusions* eCRF panels).
- Treatment regimen, including planned dose (*Treatment Assignment* and *Change of Treatment Assignment* eCRF panels).
- Body weight (*Vital Signs* eCRF panels).

The following derivations based on eCRF reported results are to be performed:

- Body weight-adjusted dose (IU/kg) is to be derived as the total units infused (IU) divided by the last available body weight (kg) prior to the infusion. Refer to Section 5.4: Handling of Missing, Unused, and Spurious Data for imputation schemes to be implemented.
- Total number of infusions in this study are determined as the count of the number of infusions, regardless of date and time, the subject had. Number of infusions are to be determined overall and by reason for infusion as well as by the treatment regimen assigned to at the time of receiving the treatment.
- The number of EDs are determined as the number of unique calendar days on which a subject received any or part of any infusion. Multiple infusions on the same day are still to be considered one ED. EDs are to be determined overall as well as for each reason an infusion is given. The number of EDs will be determined for this study and across all previous BAX 855 studies the subject participated in. EDs in this study will be derived as the number of infusions on unique calendar days in this study, while EDs from previous BAX 855 studies will be obtained as reported in the eCRF. The total EDs across all BAX 855 studies will be determined as the sum of EDs in current study and EDs in previous studies.
- The observation period for efficacy (OPE) in days in the study for subjects who never transferred to the surgery study is to be determined as:

$$OPE(Days) = (Stop\ Date - Start\ Date) + 1$$
 where "Start Date" refer to the first BAX 855 infusion in the current study and "Stop Date" to the last BAX 855 infusion in the current study. For subjects on the PK-guided regimen, first BAX 855 infusion will be the first prophylactic infusion.

• The OPE in days for subjects that did transfer to the surgery study is to be determined as:

$$OPE(Days)$$

$$= (Date\ of\ Transfer\ to\ Surgery\ Study - Start\ Date) + (Stop\ Date - Return\ Date\ to\ Current\ Study) + 1$$
where "Start\ Date" and "Stop\ Date" are\ defined\ as\ above.

• The OPE in weeks is to be determined from the OPE in days as:

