- A bleed is considered to be a minor bleed if the severity is indicated as "Mild" or "Minor".
- A bleed is considered to be a weekday bleed if the bleed occurred on a Monday, Tuesday, Wednesday, Thursday or Friday.
- A bleed is considered to be a weekend bleed if the bleed occurred on a Saturday or Sunday.
- A bleed is considered to be a morning bleed if the bleed occurred between 04:00 and 11:59.
- A bleed is considered to be an afternoon bleed if the bleed occurred between 12:00 to 17:59.
- A bleed is considered to be a night bleed if the bleed occurred between 18:00 and 03:59.
- A bleed is considered to have occurred at an unknown time if the time of a bleed is not available.
- Time since last prophylactic infusion in hours is to be derived as:
  - $Time(h) = Date/Time\ of\ Bleed\ Start\ Date/Time\ of\ Infusion$  where the start date/time of infusion refers to the last prophylactic infusion received (other than to treat a bleed) prior to the start of the bleed. Time since last prophylactic dose is to be categorized as:
    - $\circ$  <24 hours.

```
24 - <48 hours.

48 - <72 hours.

72 - <96 hours.

>96 hours.
```

• Time since previous bleed are only to be determine if a subject had multiple bleeds and is to be derived as:

```
Time(months)
= (Date/Time \ of \ Current \ Bleed
- Date/Time \ of \ Previous \ Bleed)/365.2425 \times 12
```

- A bleed is considered to be treated with BAX 855 if at least one infusion linked to the particular bleed is present in the *Study Infusion* eCRF panels. Infusions to "Maintain Hemostasis" are not to be summarized as part of treatment for bleeding episodes.
- The number of bleeds per subject overall and by location (target joint, non-target joint, joint and non-joint), causality (spontaneous/unknown and injury), severity (mild, moderate and severe) and timing (weekends, weekdays, morning, evening and afternoon) are to be determined as the count of unique bleeds in each category a subject had during the observation period.
- Annualized bleeding rate (ABR) is to be derived for each treatment regimen the subject had during the study as:

$$ABR = \frac{Number\ of\ unique\ bleeds}{OPE\ (years)\ for\ treatment\ regimen}$$

The ABR is to be analyzed using a generalized linear model fitting a negative binomial distribution with logarithmic link function. Only subjects that have 100 or more EDs are to be included in the models, where total EDs are derived as in Section 6.7: Extent of Exposure.

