The model is to be analyzed separately for each of the every 5 days and every 7 days treatment regimen. Baseline age and ABR as continuous covariate and the logarithm of the OPE in years, specific to each treatment regimen, as an offset, is to be included in the model. The following SAS® code is to be used to perform the analysis:

```
PROC GENMOD DATA = <ds>;
   MODEL <bleds> = <baseline_age> <baseline_ABR> / DIST = NEGBIN
   OFFSET = <log_OPE> LINK = LOG;
   LSMEANS <regimen> / BYLEVEL OM CL;
   ODS OUTPUT LSMEANS = <outds>;
RUN;
QUIT;
```

where <ds> refers to the input dataset, <regimen> the particular treatment regimen time of bleed, <ble> the number of bleeds during the observation period, 
 baseline\_age> the age at baseline, 
 baseline\_ABR> the ABR at baseline and <log\_OPE> the logarithm of the OPE in years, specific to the treatment regimen. Point estimates and confidence intervals obtained from the generalized linear model are to be anti-logged prior to presentation.

The twice weekly regimen and PK-tailored regimen will be analyzed together (not separately as per above model) using a generalized estimating equation (GEE) model using the following SAS® code:

```
PROC GENMOD DATA = <ds>;
   CLASS <subject> <regimen>;
   MODEL <bleeds> = <regimen> <baseline_age> / DIST = NEGBIN
   OFFSET = <log_OPE> LINK = LOG;
   REPEATED SUBJECT = <subject> / CORR = EXCH;
   LSMEANS <regimen> / BYLEVEL OM CL;
   ODS OUTPUT LSMEANS = <outds>;
RUN;
```

where <ds>, <regimen>, <bleeds>, <baseline\_age> and <log\_OPE> is define the same as before and <subject> is the subject number.

For both models above, should the model not converge a poisson model will be fitted instead. Should the non-convergence be due to all bleeds equal to zero, the estimate will be presented as zero with no confidence interval.

The model results are to be presented on the FAS and PPAS for:

- The total ABR.
- Annualized joint bleeding rate.
- Annualized non-joint bleeding rate.
- Annualized target joint bleeding rate.
- Annualized non-target joint bleeding rate.
- Annualized injury related bleeding rate.
- Annualized spontaneous/unknown bleeding rate.
- Annualized severe bleeding rate.
- Annualized moderate bleeding rate.
- Annualized minor bleeding rate.
- Annualized weekday bleeding rate.

- Annualized weekend bleeding rate.
- Annualized morning bleeding rate.
- Annualized afternoon bleeding rate.
- Annualized night bleeding rate.
- Annualized bleeding rate at unknown time.

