A figure presenting results from the generalized linear model on the total ABR is to be presented for the FAS. Figures are also to be presented showing the number of bleeds within a specific time category since previous prophylactic infusion as well as bleeds overlaid with all treatments received during the study and binding antibodies on the FAS.

ABR for the above categories is to be presented descriptively for the FAS and PPAS. Descriptive statistics on the average duration between bleeding episodes for subjects with more than one bleeding episode and characteristics of bleeding episodes (including number of infusions to treat each bleed, total dose [IU] to treat each bleed, average dose per infusion to treat each bleed [IU/kg], efficacy rating, time since previous prophylactic dose [h] and severity of each bleed) are to be presented for the FAS and PPAS as well. Summaries for bleeding episodes are to be presented by age category, presence of target joints at screening and treatment regimen at time of bleed. Descriptive summaries on the number of infusions to treat a bleed are to include the 95% confidence interval on the median number of bleeds. The 95% confidence interval on the median will be determined using the distribution-free confidence interval for the 50th percentile from the SAS® UNIVARIATE procedure.

Information on bleeding episodes including the course of target joints and ultrasound information is to be listed for the SAS.

#### 7.2 Weight-adjusted Consumption of BAX 855

Weight-adjusted consumption of BAX 855 is discussed in Section 6.7 Extent of Exposure.

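### The SAP restricts the ABR models to subjects with 100 or more cumulative EDs, labels the results FAS, and does not declare the change from the protocol

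*SAP*

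**What the plan says.** Protocol 13.2.1 and 13.2.2 make the full analysis set identical to the safety set, which needs one infusion, and add: "All efficacy analyses will be performed on the full analysis set". Protocol 13.4.1.2 specifies the spontaneous-ABR model with a log follow-up offset and no exposure condition. Protocol 10.6 says of subjects who leave early that "the data collected up to the time of discontinuation will be used in the analysis".

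The SAP keeps the same population. Its safety set (4.2) "is to comprise all subjects in the ENR with at least one BAX 855 infusion", and its FAS (4.3) "is to comprise of all subjects in the SAS". Section 7.1 then adds, for the ABR models: "Only subjects that have 100 or more EDs are to be included in the models". The ED count is cumulative. Under SAP 6.7, "The total EDs across all BAX 855 studies will be determined as the sum of EDs in current study and EDs in previous studies", and any calendar day with an infusion counts, whatever the reason for it.

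The label does not change to match. SAP 7.1 continues: "The model results are to be presented on the FAS and PPAS for" a list that includes the spontaneous/unknown rate. The same section says "ABR for the above categories is to be presented descriptively for the FAS and PPAS", with no ED threshold stated.

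SAP 5.7 lists two changes from the protocol analysis: some imputation, and separate modelling of the 5-day and 7-day regimens. The ED restriction is not among them, and the revision history does not mention it. SAP 4.4 names failure to reach 100 EDs as a possible major deviation, to be discussed before any exclusion from the PPAS.

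**The concern.** A model fitted only to subjects with 100 or more EDs is not an FAS analysis. As written, the restriction applies automatically in the FAS model, whereas for the PPAS it is only a matter for discussion.

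The restriction also conditions on something that happens after baseline and can be related to the outcome. Protocol 9.3 allows withdrawal for a life-threatening bleed, an inhibitor that cannot be managed, or repeated use of another FVIII product. Losing such subjects could lower the modelled ABR. In the other direction, bleed-treatment days count as EDs. Among subjects who stop when prophylaxis alone would leave them short of 100, those who bleed more are likelier to be kept, which could raise it.

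At stake is the prespecified model mean and 95% CI for the co-primary efficacy measure: a reader would take it to describe everyone treated.

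**Working it through.** **1. Who is in the analysis**

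| Place | Population |
|---|---|
| Protocol 13.2.1, 13.2.2 | At least 1 infusion; all efficacy analyses |
| Protocol 13.4.1.2 | No ED condition in the ABR model |
| SAP 4.2, 4.3 | At least 1 infusion |
| SAP 7.1, models | At least 100 cumulative EDs, labelled FAS and PPAS |
| SAP 7.1, descriptive ABR | FAS and PPAS, no ED condition stated |
| SAP 5.7 | Restriction not listed |

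**2. Does the restriction secure adequate follow-up?** No. EDs are summed over all BAX 855 studies, while the offset is the observation period (OPE) in this study. A transitioning subject who already has 100 EDs stays in the model after leaving within weeks. A naïve subject on twice-weekly dosing with 95 EDs is dropped after 95/2 = 47.5 weeks. The log(OPE) offset already handles unequal follow-up.

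The restriction can also fall unevenly by regimen. Days in this study to reach 100 EDs on prophylaxis alone:

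| Prior EDs | Twice weekly | Every 5 days | Every 7 days |
|---|---|---|---|
| 0 | 100/2 × 7 = 350 | 100 × 5 = 500 | 100 × 7 = 700 |
| 50 | 175 | 250 | 350 |

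**3. Share excluded.** The plan enrols about 250 to obtain 200 evaluable subjects: 1 - 200/250 = 20%, and 200/0.80 = 250. No dropout rate is stated, and the 250 counts consented subjects, some of whom may never be infused. So 20% of the FAS is taken as an upper assumption, with 5% and 10% also shown.

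**4. Shift in the pooled rate.** Let f be the share of the FAS excluded and r the ABR of excluded relative to included subjects. Assume excluded subjects have half the follow-up. Then

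shift = [(1 - f) + 0.5f] / [(1 - f) + 0.5f·r] - 1.

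For f = 0.20, r = 3: 0.90/1.10 - 1 = -18.2%.

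| f | r = 0.5 | r = 1 | r = 1.5 | r = 2 | r = 3 |
|---|---|---|---|---|---|
| 5% | +1.3% | 0 | -1.3% | -2.5% | -4.9% |
| 10% | +2.7% | 0 | -2.6% | -5.0% | -9.5% |
| 20% | +5.9% | 0 | -5.3% | -10.0% | -18.2% |

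**5. Shift under the planned type of model.** Negative binomial model with exposure offset; 200 FAS subjects, 300 replicates, ABR 1.5 per year in included subjects, dispersion k = 1 (all assumed). Entries are restricted estimate / all-FAS estimate; at r = 1 the shift is 0 within simulation error.

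| f | r = 0.5 | r = 2 | r = 3 |
|---|---|---|---|
| 5% | 1.50/1.47 (+1.9%) | 1.50/1.55 (-3.6%) | 1.50/1.62 (-7.2%) |
| 10% | 1.50/1.44 (+3.7%) | 1.50/1.62 (-7.2%) | 1.50/1.73 (-13.2%) |
| 20% | 1.48/1.37 (+8.0%) | 1.51/1.74 (-13.3%) | 1.50/1.98 (-24.3%) |

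The shifts exceed the pooled ones because the negative binomial fit weights a subject by t/(1 + kμt), where t is follow-up and μ the fitted rate. With μ = 1.74, half a year counts 0.5 × 2.74/1.87 = 0.73 of a full year rather than 0.5. For f = 20%, r = 2 this gives (0.8 + 0.2 × 0.73)/(0.8 + 0.2 × 0.73 × 2) - 1 = -13%, in line with the simulation.

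**6. Sign.** A second simulation (mean ABR 2, k = 1, one year) let dropout depend on bleeding. The restricted/all-FAS ratio fell from 0.95 (about 9% excluded) to 0.86 (about 22% excluded). Dropout unrelated to bleeding gave 1.00 to 1.01. In a deliberately extreme case, follow-up was cut so that prophylaxis alone gave 104 × 0.94 = 97.8 EDs. Bleed-treatment days then carried bleeders over the line, 74% of subjects were excluded, and the ratio was 2.6. That case shows only that the sign can reverse.

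**The case against.** The strongest defence is that this is a deliberate evaluable-subject analysis that lacks a label. The sample size rests on subjects with 100 EDs, Protocol 6.3 expects every subject to reach that number, and the inhibitor analysis in SAP 8.3 has a similar rule. This explains the restriction but does not make its result an FAS result. SAP 8.3 also states its subset openly and keeps every inhibitor case whatever the ED count; the ABR rule drops an early leaver's bleeds and follow-up together.

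Several points stand:

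- Subjects are meant to continue to at least 100 EDs and prior EDs count, so few may be excluded and the shift may be small.
- Reaching 100 sooner selects nobody among completers. The upward mechanism works only among subjects who would otherwise stop short.
- Some withdrawal reasons, such as pregnancy or need for another PEGylated drug, have no evident link to bleeding.
- Protocol 10.6 is weak support, because the descriptive ABR, exposure and AE summaries also use early leavers' data. The direct conflict is with 13.2.2.
- The Output Templates are not supplied and might show the N or a footnote. The SAP's Russian Federation age limits are absent from the supplied protocol, so it may follow another protocol version. Neither removes the contradiction inside the SAP.
- Sampling error is of similar size. With 180 subjects, one year each, ABR 1.5 and k = 1, the standard error of the log rate is √[(1/1.5 + 1)/180] = 0.096, so the 95% CI is about -17% to +21%. Every 5% and 10% scenario above lies inside that. A bias is not covered by the interval, however; it moves the interval.

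**Conclusion.** The point holds. SAP 7.1 contradicts the SAP's own FAS definition and Protocol 13.2.2, and SAP 5.7 does not declare the change. That part rests on the text alone.

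The bias is a possibility, with size and direction unknown. The illustrated range of +5.9% to -18.2% (pooled) or +8.0% to -24.3% (negative binomial) depends wholly on the assumed share excluded, rate ratio, half follow-up and, for the model, ABR and dispersion. If excluded subjects bleed at the same rate as the rest, only precision is lost.

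The consequence is bounded. The study is uncontrolled, has no ABR hypothesis or threshold, and already plans descriptive ABR on the FAS, where a reader could see a discrepancy. This should be fixed, but no pass/fail conclusion can turn on it.

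**What to change.** Delete the sentence in SAP 7.1 that restricts the models. Fit both ABR models on all FAS subjects with OPE above zero, using the log(OPE) offset already specified. If the 100-ED subset is wanted, keep it as a labelled sensitivity analysis, declare it in SAP 5.7, and report by regimen the number of FAS subjects it excludes and their descriptive ABR.

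Naming and declaring the subset while leaving it as the main model would cure the inconsistency inside the SAP. It would not cure the selection or the departure from Protocol 13.2.2. Nor does the full-FAS fit remove every effect of bleed-related dropout: in the second simulation it gave 1.93 to 1.83 against a true mean of 2.0. The restricted fit was further off, at 1.83 to 1.58.

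Cost: one SAP sentence, one entry in SAP 5.7 if the subset is kept, and one extra model run. No new data are needed.

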13.4.1.2 Primary Efficacy Outcome Measure

The spontaneous ABR will be assumed to have a negative binomial distribution, and the mean ABR (95% CI) will be estimated using a general estimating equation (GEE) model framework (with a logarithmic link function which is the default for the negative binomial distribution) with treatment regimen as a fixed effect, subject effect as a random effect, age at baseline as a continuous covariate, and the logarithm of follow-up time (in years) as an offset.

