## 5.7 Changes from the Planned Statistical Analysis in Protocol

The following changes from the analyses planned in the Protocol have been made:

- The protocol mentions that no missing data is to be imputed. Imputations for certain missing data items have been allowed for though (refer to Section 5.4: Handling of Missing, Unused, and Spurious Data).
- The protocol mentions one generalized estimating equation (GEE) model to be fit for ABR. Due to the difference in treatment regimens between protocol amendments, this has been adjusted to model twice weekly fixed dose regimen and PK-tailored regimen separately from the every 5 and 7 day treatment regimens.

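### The SAP 7.1 code for the every-5-day and every-7-day ABR requests LS-means of a regimen term the model does not contain, and its baseline-ABR covariate is a protocol departure not listed in SAP 5.7

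*SAP*

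**What the plan says.** Protocol 13.4.1.2 describes one model for spontaneous ABR: negative binomial, log link, GEE framework, with treatment regimen, subject, "age at baseline as a continuous covariate, and the logarithm of follow-up time (in years) as an offset".

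SAP 5.7 declares a split of that model. Because regimens changed between amendments, "this has been adjusted to model twice weekly fixed dose regimen and PK-tailored regimen separately" from the every-5-day and every-7-day regimens. It names no change of covariates.

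SAP 7.1 then prints two blocks of code and says each is to be used.

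- **Every 5 days and every 7 days.** "The model is to be analyzed separately for each of the every 5 days and every 7 days treatment regimen". The covariates are given as "Baseline age and ABR as continuous covariate and the logarithm of the OPE in years", the last being the offset. The model line is "MODEL <bleds> = <baseline_age> <baseline_ABR> / DIST = NEGBIN". There is no CLASS statement. The output request is "LSMEANS <regimen> / BYLEVEL OM CL", and the LS-means table is what is saved.
- **Twice weekly and PK-tailored.** These are fitted together with "CLASS <subject> <regimen>" and "MODEL <bleeds> = <regimen> <baseline_age> / DIST = NEGBIN", with a REPEATED statement and the same LSMEANS line.

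If either model fails to converge, a Poisson model replaces it. Results go to 16 bleed categories, on both the FAS and the PPAS.

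**The concern.** There are two separate faults in the first block.

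The first is mechanical. The only estimate the block saves is the LS-mean of an effect the model does not contain. A programmer following the SAP gets no model-based ABR for two of the four modelled regimens and has to choose a repair that the SAP does not specify.

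The second concerns content. Baseline ABR enters the model for these two regimens and no other. A reader comparing model-based ABRs across regimens would be comparing figures adjusted for different covariates, and would not learn from SAP 5.7 that the protocol's model had been changed in this way.

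**Working it through.** The documents give no figure for this model, so the check is a comparison of the two blocks, a short piece of algebra and an illustration on simulated data.

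**1. The blocks side by side**

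| Element | Every 5 / every 7 days | Twice weekly and PK-tailored |
|---|---|---|
| CLASS | none | subject, regimen |
| Right-hand side of MODEL | baseline age, baseline ABR | regimen, baseline age |
| LSMEANS | regimen | regimen |
| Saved output | LS-means table | LS-means table |

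An LS-mean is a linear combination of the fitted parameters for a classification effect. The first fit has no regimen parameter, so there is nothing to combine. The second block shows what was needed. The misspelt response name in the first MODEL line is a placeholder and does not matter.

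**2. Number of estimates affected**

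2 regimens × 16 categories × 2 analysis sets = 64 model-based estimates.

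**3. Is the intended quantity obtainable?**

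Add a one-level regimen term:

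log rate = α + ρ + β₁·age + β₂·baseline ABR.

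α and ρ are not separately identified, but α + ρ is. The LS-mean, (α + ρ) + β₁·(mean age) + β₂·(mean baseline ABR), uses only that sum and is estimable. Without a regimen term, the intercept takes the place of α + ρ, and the prediction at the covariate means is the same quantity.

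Numerical check on one simulated regimen (assumed: 25 subjects, negative binomial dispersion 1/1.5 = 0.67, mean baseline ABR 8, on-study rate about 2 per year):

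- The design with the one-level term has 4 columns and rank 3.
- Exponentiated LS-mean with the one-level regimen term: 1.769.
- Prediction at the covariate means without it: 1.769.

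**4. Does the extra covariate change the answer?**

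The simulation used the same assumptions with 2,000 subjects. The slope is the change in log rate per unit of baseline ABR. The documents give no value, so three were assumed.

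| Assumed slope | Age only | Age + baseline ABR | Ratio |
|---|---|---|---|
| 0 | 1.909 | 1.908 | 1.909/1.908 = 1.00 |
| 0.03 | 1.981 | 1.921 | 1.981/1.921 = 1.03 |
| 0.06 | 2.184 | 1.889 | 2.184/1.889 = 1.16 |

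If baseline ABR does not predict on-study bleeding, the choice is immaterial. If it does, the two adjusted means differ.

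**5. Is the covariate defined?**

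SAP 7.1 calls it only the ABR at baseline. SAP 6.2 mentions an average ABR over the previous three to six months from the treatment-history form, but 7.1 does not point to it. Under the protocol's note to Section 8.7.3, subjects who stay on these regimens follow the transitioning-subject procedures, whereas Protocol 8.2 describes collecting bleeding history at screening for naïve subjects. SAP 5.4 has no imputation rule for this variable, so a subject without a value would drop out of the fit.

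**The case against.** The strongest reply is that this is a slip in sample code. The text of SAP 7.1 gives the distribution, link, covariates, offset and back-transformation, so a competent programmer would see what is meant. That stands in part: the intended estimate is recoverable. But the SAP says this code is to be used, and its only fallback answers a different problem.

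A second reply is that baseline ABR is not hidden, since SAP 7.1 names it in the text, the model line and the variable key. That is correct. What is missing is its listing in SAP 5.7 as a change from the protocol.

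A third is that the reach is small. These regimens continue only for subjects already on them before protocol amendment 4, the protocol's two groups are fixed dose and PK-tailored, and SAP 7.1 also reports ABR descriptively, with bleeding summaries by regimen. This also stands and limits the weight of the point.

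Some stronger readings are not supported:

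- A reader might infer that the ABR for these regimens cannot be estimated, or that a regimen term cannot be added when a fit holds only one regimen. Step 3 shows otherwise.
- A reader might infer that the baseline-ABR covariate causes the failure. It plays no part in it.
- A reader might object to evaluating a log-link model at mean covariates. The GEE block does this for age as well, and the protocol does not require averaging of predicted rates, so it is the plan's convention and not a fault of this block.

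**Conclusion.** The point holds in a limited form. As printed, the code for the every-5-day and every-7-day regimens does not produce the requested ABR estimate in any bleed category, spontaneous/unknown included. This follows from the structure of the block and its contrast with the second block, and needs no numerical assumption.

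Separately, the covariate set for these regimens differs from the protocol's and from the GEE block's, and SAP 5.7 does not say so. How far this moves the estimates cannot be determined from the documents. The ratios of 1.00 to 1.16 in step 4 rest entirely on assumed inputs and show only that the choice need not be neutral. The documents also do not say how many subjects are on these regimens.

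The model for the twice-weekly and PK-tailored regimens has regimen in CLASS and MODEL, so the co-primary efficacy analysis as a whole is not undermined. This should be corrected, and the correction is cheap.

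**What to change.** In the every-5-day/every-7-day block of SAP 7.1:

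1. Add `CLASS <regimen>` and put `<regimen>` in MODEL, keeping the separate fit per regimen. Alternatively, replace LSMEANS with an ESTIMATE at the covariate means and save that table instead.
2. Drop `<baseline_ABR>`, so that the right-hand side matches "MODEL <bleeds> = <regimen> <baseline_age> / DIST = NEGBIN" and the protocol's covariates. If the sponsor wants the baseline-ABR adjustment, keep it only as a sensitivity model listed in SAP 5.7. State its source and look-back period, including for transitioning subjects, and what happens when it is missing.

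The cost is a few lines of SAP text and code, with no new data. Dropping the covariate gives up any precision it would have added. Pooling the two regimens or changing the estimator is not needed to repair the fault.
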